10.3.2 Intensity of Adverse Events

The intensity of adverse changes in physical signs or symptoms will be graded according to the CTCAE version 4.0.3. For all other adverse events not described in the CTCAE, the intensity will be assessed by the Investigator using the following categories (see Table 8):

Mild (Grade 1) – transient or mild discomfort; no limitation in activity; no medical intervention/therapy required.

Moderate (Grade 2) – mild to moderate limitation in activity, some assistance may be needed; no or minimal medical intervention/therapy required.

Severe (Grade 3) – marked limitation in activity, some assistance usually required; medical intervention/therapy required, hospitalization is possible.

Life-threatening (Grade 4) – extreme limitation in activity, significant assistance required; significant medical intervention/therapy required, hospitalization or hospice care probable.

Death (Grade 5) – the event resulted in death

| Grade | Severity | Alternate Description ^a |
|-------|--|--|
| 1 | Mild (apply event-specific | Transient or mild discomfort |
| | NCI-CTCAE grading criteria) | (<48 hours); no interference with the subject's daily activities; no medical intervention/therapy required |
| 2 | Moderate (apply event-specific NCI-CTCAE grading criteria) | Mild to moderate interference with the subject's daily activities; no or minimal medical intervention/therapy required |
| 3 | Severe (apply event-specific NCI-CTCAE grading criteria) | Considerable interference with the subject's daily activities; medical intervention/therapy required; hospitalization possible |
| 4 | Very severe, life threatening, or disabling (apply event-specific NCI-CTCAE grading criteria) | Extreme limitation in activity; significant medical intervention/therapy required, hospitalization probable |
| 5 | Death related to AE | |

 Table 8. Adverse Event Grading (Severity) Scale

Note: Regardless of severity, some events may also meet regulatory serious criteria. Refer to definitions of an SAE. Use these alternative definitions for Grade 1, 2, 3, and 4 events when the

observed or reported AE is not in the NCI-CTCAE listing.

10.3.3 Action Taken with Study Drug

The action the Investigator took with study drug as a result of the event should be recorded as one of the following:

None – No action was taken with regard to the study drug as a result of the adverse event.

Interrupted – Study drug was stopped due to the adverse event, but was later resumed at the same dose.

Dose decreased – The dose of study drug was decreased as a result of the adverse event.

Permanently discontinued – The subject was withdrawn from the study due to the adverse event.

Only one item should be chosen. If multiple actions apply, the following "worst case" scenario hierarchy should be used to determine the preferred entry:

Discontinued > dose decreased > therapy interrupted.

10.3.4 Definition of Outcome

The outcome of the AE should be recorded as one of the following:

Resolved without sequelae – The subject fully recovered from the adverse event with no observable residual effects.

Resolved with sequelae – The subject recovered from the adverse event with observable residual effects.

Not resolved – The adverse event was present at the time of last observation.

Death – The subject died as a result of the adverse event.

10.4 Immediately Reportable Events

10.4.1 Serious Adverse Events

Taiho Reporting Requirements

All SAEs, as well as events of overdose, medication error, pregnancy (whether serious or nonserious), to Taiho Oncology pharmacovigilance or designee within 24 hours of awareness. SAEs will be reported to Taiho Oncology either by e-mail at [contact] or via fax at [contact]. Any SAE inquiries to Taiho Oncology may be done by hotline phone at [contact]. **NOTE:** The hotline phone number is for inquiries only and not to report SAEs.

At the time of the annual DSUR (data-lock point), a list of all AEs which led to discontinuation, subjects with fatal events, and demographic information for all subjects exposed to TAS-102 must all be submitted to Taiho.

UFHCC PMO and DISC Reporting Requirements

Serious adverse events (SAE's) must be reported to UFHCC Project Management Office (PMO; [contact]) and entered into OnCore within 24 hours of discovery of the event. If only limited details are known, these should be reported within that time frame and follow up reports can be submitted for elaboration, clarifications, or corrections. Any email correspondence must be kept in the trial file at the study site. The site investigator is responsible for informing the IRB and/or the Regulatory Authority of the SAE as per local requirements. SAEs must also be reported to the UFHCC DISC Safety Team within **5 days** of discovery of the event. The original copy of the SAE Report and any email correspondence must be kept within the Trial Master File at the study site. The site investigator is responsible for informing the IRB and/or the Regulatory Authority of the reported must be kept within the Trial Master File at the study site. The site investigator is responsible for informing the IRB and/or the Regulatory Authority of second must be kept within the Trial Master File at the study site. The site investigator is responsible for informing the IRB and/or the Regulatory Authority of the second must be kept within the Trial Master File at the study site. The site investigator is responsible for informing the IRB and/or the Regulatory Authority of the SAE as per local requirements.

Follow-up information will be submitted to the UFHCC PMO ([contact]), stating that this is a follow-up to a previously reported SAE and giving the date of the original report.

Each re-occurrence, complication, or progression of the original event should be reported as a follow-up to that event regardless of when it occurs. The follow-up information should describe whether the event has resolved or continues, if and how it was treated, and whether the participant continued or withdrew from study participation. PMO will confirm that the event and any necessary follow-ups are reported to the UFHCC Data and Safety Integrity Committee (DISC), Taiho Oncology, and any other regulatory authorities as required.

All AEs that do not meet any of the criteria for serious should be regarded as non-serious AEs.

Institution SAE and Pregnancy Reporting Information

SAEs and pregnancies must be reported to the UFHCC CRO Project Management Office (PMO), or assigned designee at:

Email: [contact]

As well as entered in OnCore, the study CTMS.

10.4.2 Other Events Requiring Immediate Reporting

Pregnancies, overdoses, and medication errors should be documented and reported per the SAE reporting guidelines in section 10.4.1 above.

10.4.2.1 Pregnancy

If a subject becomes pregnant while in the study, the study treatment must be immediately discontinued. Pregnancy information for a female subject should be reported within 24 hours from the time the Investigator first becomes aware of a pregnancy or its outcome. This should be performed by completing a Pregnancy Form and faxing it to Taiho Pharmacovigilance or designee.

New and/or corrected information regarding the pregnancy obtained after submitting the initial Pregnancy Form must be submitted by faxing an updated Pregnancy Form to Taiho Pharmacovigilance or designee.

If outcome of the pregnancy is a stillbirth, congenital anomaly/birth defect, or a serious event in the mother, report as an SAE to Taiho Pharmacovigilance or designee.

All pregnancies, regardless of outcome, must be also reported to the UFHCC PMO ([contact]) and DISC, including pregnancies that occur in the female partner of a male study subject. All pregnancies must be followed to outcome

10.4.2.2 Overdose

An overdose with TAS-102 is defined as:

- Taking a dose beyond the recommended dose in one day or beyond the recommended total dose in each cycle.
- An accidental or intentional overdose with TAS-102 regardless of whether it is associated with an AE (even if not fulfilling a seriousness criterion)

These events are to be captured as an AE on the eCRF and reported to Taiho Pharmacovigilance or designee **within 24 hours** from the time the Investigator first becomes aware of its occurrence following the same process as described for the SAEs.

There is no known antidote available in case of TAS-102 overdose. Overdose should be managed aggressively with close monitoring and administration of prophylactic and symptomatic therapies to prevent or correct potential side effects.

An accidental or intentional overdose for concomitant medication should only be reported if it is associated with an AE.

Although overdose (dose variance of >10%) and cancer are not always serious by regulatory definition, these events should also be reported to the UFHCC PMO ([contact]) and DISC in an expedited manner. In case the overdose did not result in any adverse event, the Investigator should report this as "overdose, no adverse event" on the SAE form and provide the intended amount, as well as the actual amount, of drug administered. In the event of overdose or exaggerated response, appropriate supportive measures should be employed. Actual treatment should depend on the severity of the clinical situation and the judgment and experience of the treating physician.

10.4.2.3 Medication Error

A medication error is defined as any accidental incorrect administration of a medicinal product. The error may be related to the administration of a wrong medication, nature of the medication, route of administration, dosage or frequency of the treatment as specified in this protocol (including omission of one or more administrations).

- Medication errors with study medication and concomitant medication treatment will not be recorded in the eCRF unless they result in an AE or overdose.
- Medication errors with study medication that result in an overdose will be captured as an AE in the eCRF.
- Medication errors with study medication that do not result in an AE should be handled as follows:
 - If it results in the omission of an administration, an incorrect dose (relative to that specified in this protocol), or the administration of more than the prescribed dose (but does not meet the overdose criteria), it will be identified through the

recording of study drug accountability data in the eCRF and does not need to be reported as an AE.

• If it results in an overdose, incorrect route of administration, or administration of an incorrect study drug, it will be reported as an AE.

Based on the above criteria, medication errors that are captured as an AE on the eCRF should be reported to UFHCC PMO ([contact]) and Taiho Pharmacovigilance or designee **within 24 hours** from the time the Investigator first becomes aware of its occurrence following the same process as described for the SAEs even if it does not meet any of the criteria of an SAE.

10.5 IND Safety Reports Unrelated to this Trial

IND safety reports not occurring on this trial but involving the study intervention received from outside sources will be forwarded to participating sites for submission to their Institutional Review Boards per their guidelines.

11 ASSESSING SAFETY

11.1 Specfications of Safety Analysis

Safety assessments will consist of monitoring and recording protocol-defined adverse events (AEs) and serious adverse events (SAEs); measurement of protocol-specified hematology, clinical chemistry, and urinalysis variables; measurement of protocol-specified vital signs; and other protocol-specified tests that are deemed critical to the safety evaluation of the study drug(s).

Death as a result of disease progression is only to be assessed as efficacy measures and not as AEs or SAEs unless the events that led to death met the serious criteria.

The terms "severe" and "serious" are not synonymous. Severity (or intensity) refers to the grade of a specific AE, e.g., mild (Grade 1), moderate (Grade 2), or severe (Grade 3) myocardial infarction. "Serious" is a regulatory definition (see previous definition) and is based on subject or event outcome or action criteria usually associated with events that pose a threat to a subject's life or functioning. Seriousness (not severity) serves as the guide for defining regulatory reporting obligations from the Sponsor to applicable regulatory authorities.

Severity and seriousness should be independently assessed when recording AEs and SAEs on the CRF.

11.2 Safety Analysis

Subjects will be examined and graded each cycle for subjective/objective evidence of developing toxicity according to NCI-CTCAE version 4.03 toxicity criteria. Incidence tables will be generated to summarize incidence of subjects reporting at least one episode of each specific adverse event, incidence of adverse events causing withdrawal, and incidence of serious adverse events. Subjects will have laboratory values assessed prior to and on Day 15 of each cycle.

Adverse event data and corresponding toxicity grades during treatment and during long-term follow-up will be summarized in the form of tables. Incidence tables will be generated to summarize incidence of subjects reporting at least one episode of each specific adverse event, incidence of adverse events causing withdrawal and incidence of serious adverse events. The total number of episodes for each event reported (Frequency Table), the severity and attribution to study therapy of each episode reported (Severity Table and Attribution Table) will also be displayed. Listings of adverse events by subjects will include the time to onset, the duration of each event, the severity of each event, and the relationship of the event to study therapy, whether it was a serious event, and whether it caused withdrawal. Safety data will be summarized for the overall subject group and by dose levels. Dose-toxicity curves will be fitted to the final data to estimate the toxicity rates of each dose levels.

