- WOCBP include any woman who has experienced menarche and who has not undergone successful surgical sterilization (hysterectomy, bilateral tubal ligation, or bilateral oophorectomy) or who is not post-menopausal. Post-menopause is defined as:
 - Amenorrhea that has lasted for ≥ 12 consecutive months without another cause, or
 - For women with irregular menstrual periods who are taking hormone replacement therapy (HRT), a documented serum follicle-stimulating hormone (FSH) level of greater than 35 mIU/mL.
- Males with female partners of child-bearing potential must agree to use physician-approved contraceptive methods (*e.g.*, abstinence, condoms, vasectomy) throughout the study and should avoid conceiving children for 3 months following the last dose of study drug.
- Baseline laboratory values (bone marrow, renal, hepatic) must include:
 - Adequate bone marrow function:
 - Absolute neutrophil count $\geq 1500/$ mm³
 - Platelet count $\geq 75,000/$ mm³
 - HGB equal to or greater than 7g/dL
 - Renal function:
 - Serum creatinine ≤ 1.5 mg
 - Hepatic function:
 - Total bilirubin $\leq 1.5 \text{ mg/dL}$
 - AST and ALT equal to or less than 3 times the upper limit of normal for patients without hepatic involvement, or AST and ALT equal to or less than 5 times the upper limit of normal for patients with hepatic involvement
 - Serum calcium $\leq 12 \text{ mg/dl}$

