g. h. CT of the chest, abdomen and pelvis or CT of the chest and MRI of the abdomen and pelvis are allowed. Consistent imaging modality should be used throughout the study. Imaging should be performed every 8 weeks (+/- 7 days) beginning with Cycle 3 until disease progression.

H&P is required at 30 days (+7 days) following the last dose of study drug. Additional H&Ps are required as needed to follow ongoing AEs.

Adverse events should be followed for 30 days after the last dose of protocol therapy or until the initiation of subsequent treatment. AEs continuing > 30 days should be monitored until resolution.

Subjects or providers should be contacted every 3 months to assess survival status and subsequent therapies.

TAS-102 (Lonsurf[®]) is administered orally twice daily within one hour of completion of morning and evening meals on Days 1 through 5 and Days 8 through 12 of each 28-day cycle.

For CBC w/diff to be obtained at Day 15 of each cycle, notify the investigator if any of the following parameters are observed m. in the lab results: 1) ANC \leq 500 µL, 2) platelets < 50 thou/mm³, or 3) Hgb < 7 g/dL.

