9 STUDY DRUG INFORMATION

- 9.1 Study Drug Name TAS-102 (Lonsurf[®])
 - 9.1.1 Drug Supply TAIHO Oncology, Inc.
 - 9.1.2 Contraindications: none
 - 9.1.3 Special Warnings and Precautions for Use

Myelosuppression

In Study 1, LONSURF[®] caused severe and life-threatening myelosuppression (Grade 3-4) consisting of anemia (18%), neutropenia (38%), thrombocytopenia (5%) and febrile neutropenia (3.8%). One patient (0.2%) died due to neutropenic infection. In Study 1, 9.4% of LONSURF[®]-treated patients received granulocyte-colony stimulating factors.

Obtain complete blood counts prior to and on Day 15 of each cycle of LONSURF[®] and more frequently as clinically indicated. Withhold LONSURF[®] for febrile neutropenia, Grade 4 neutropenia, or platelets less than 50,000/mm³. Upon recovery, resume LONSURF[®] at a reduced dose.

Embryo-Fetal Toxicity

Based on animal studies and its mechanism of action, LONSURF[®] can cause fetal harm when administered to a pregnant woman. Trifluridine/tipiracil caused embryo-fetal lethality and embryo-fetal toxicity in pregnant rats when orally administered during gestation at dose levels resulting in exposures lower than those achieved at the recommended dose of 35 mg/m² twice daily.

Advise pregnant women of the potential risk to the fetus. Advise females of reproductive potential to use effective contraception during treatment with LONSURF[®].

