9.1.4 Adverse Event Profile

| Table 7. Per Patient Incidence of Adverse Drug Reactions (≥5%) in Study 1** Occur | ring |
|---|------|
| More Commonly (>2%) than in Patients Receiving Placebo | _ |

| Adverse Reactions | | LONSURF® | | Placebo | | |
|--|-------------|------------------|------------|---------|------------|--|
| | | (N=533) | | (N=265) | | |
| All Grades | Grades 3 | 3-4 | All Grades | | Grades 3-4 | |
| Gastrointestinal | disorders | | | | | |
| Nausea | 48% | 2% | 24% | | 1% | |
| Diarrhea | 32% | 3% | 12% | | <1% | |
| Vomiting | 28% | 2% | 14% | | <1% | |
| Abdominal | 21% | 2% | 18% | | 4% | |
| pain | | | | | | |
| Stomatitis | 8% | <1% | 6% | | 0% | |
| General disorde | rs and adm | inistration site | conditions | | | |
| Asthenia/fatigu | 52% | 7% | 35% | | 9% | |
| e | | | | | | |
| Pyrexia | 19% | 1% | 14% | | <1% | |
| Metabolism and | nutrition d | lisorders | | | | |
| Decreased | 39% | 4% | 29% | | 5% | |
| appetite | | | | | | |
| Nervous system disorders | | | | | | |
| Dysgeusia | 7% | 0% | 2% | | 0% | |
| Skin and subcutaneous tissue disorders | | | | | | |
| Alopecia | 7% | 0% | 1% | | 0% | |

**Study 1: a randomized (2:1), double-blind, placebo-controlled trial in which 533 patients (median age 63 years; 61% men; 57% White, 35% Asian, 1% Black) with previously treated metastatic colorectal cancer received LONSURF[®] as a single agent at a dose of 35 mg/m²/dose administered twice daily on Days 1 through 5 and Days 8 through 12 of each 28-day cycle. The mean duration of LONSURF[®] therapy was 12.7 weeks

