10.3 Documenting and Reporting of Adverse Events by Investigator

All adverse events must be fully recorded in the subject's case record form.

Documentation must be supported by an entry in the subject's file. A laboratory test abnormality considered clinically relevant, e.g., causing the subject to withdraw from the study, requiring treatment or causing apparent clinical manifestations, or judged relevant by the investigator, should be reported as an adverse event. Each event should be described in detail along with start and stop dates, severity, relationship to investigational product, action taken and outcome.

Every attempt should be made to describe the adverse event in terms of a diagnosis that encompasses the component signs and symptoms. If only nonspecific signs or symptoms are present, then these should be recorded as separate diagnoses on the pages of the case report form.

All subjects who have adverse events, whether considered associated with the use of study drug or not, must be monitored to determine the outcome. The clinical course of the adverse event will be followed according to accepted standards of medical practice, even after the end of the period of observation, until a satisfactory explanation is found or the Principal Investigator considers it medically justifiable to terminate follow-up. Should the adverse event result in death, a full pathologist's report should be supplied, if possible.

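### Section 11.2 defines only adverse-event tables, so a Day 15 Grade 3 neutropenia that recovers can go uncounted although the counts are collected

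*Combined protocol and SAP*

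**What the plan says.** Section 9.1.3 puts myelosuppression first among the warnings. In Study 1 the Grade 3-4 rates were neutropenia 38%, anemia 18%, thrombocytopenia 5% and febrile neutropenia 3.8%. The largest Grade 3-4 rate on drug in Table 7 (9.1.4) is 7%, for asthenia/fatigue.

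The counts are collected. Table 4 schedules a CBC with differential before each cycle and on Day 15. Section 11.1 lists "measurement of protocol-specified hematology, clinical chemistry, and urinalysis variables" among the safety assessments, and 11.2 repeats that "Subjects will have laboratory values assessed prior to and on Day 15 of each cycle".

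The outputs defined in 11.2 are incidence, frequency, severity and attribution tables and by-subject listings, all of adverse events. The section also says in general terms that safety data will be summarized overall and by dose level, without naming any laboratory variable or method. Sections 12.2 and 12.3 add no laboratory summary.

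The recording rule is in 10.3. What should be reported is "A laboratory test abnormality considered clinically relevant, e.g., causing the subject to withdraw from the study, requiring treatment or causing apparent clinical manifestations", or one that the investigator judges relevant. Section 10.1.1 likewise limits laboratory findings to those considered clinically significant.

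Table 4 note m governs the Day 15 count: "For CBC w/diff to be obtained at Day 15 of each cycle, notify the investigator if any of the following parameters are observed". The levels are ANC 500 or below, platelets below 50 thousand/mm³ and hemoglobin below 7 g/dL.

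**The concern.** Safety and tolerability is a secondary endpoint (2.2), and 12.3 promises toxicity rates with exact 95% intervals. Section 11.2 also plans dose-toxicity curves. If these draw on adverse-event records, the rate reported for the most frequent listed severe harm reflects two things at once: how often neutrophils fell to Grade 3-4, and how often an investigator thought an asymptomatic fall worth reporting. The second can differ between investigators, and an exact interval does not reflect it. A reader could take a low adverse-event rate as evidence of mild myelosuppression when it partly reflects recording practice. Objective counts that would settle the matter are collected but have no defined summary.

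**Working it through.** The plan states no figure to reproduce. The main check is whether anything in the protocol obliges a Day 15 Grade 3 neutropenia to enter the adverse-event tables.

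**Step 1: follow one subject.** Take a Day 15 ANC above 500/mm³ but in the Grade 3 range, without fever, that has recovered to at least 1,500/mm³ by the next cycle.

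- Alert (Table 4 note m): acts at ANC 500 or below. Not triggered.
- Within-cycle hold (5.4.3): ANC below 500/mm³ or febrile neutropenia. Not triggered. Day 15 also falls in the Day 13-28 rest period (5.1), so there is no dose to hold.
- Start of next cycle (5.4.3): requires ANC of at least 1,500/mm³. Met, so no delay.
- Dose reduction (5.4.3): for neutropenia, follows febrile neutropenia or Grade 4 neutropenia with more than a 1-week delay. Not triggered.
- Grade boundary: 6.2 places Grade 4 neutropenia at ANC below 500/mm³, so Grade 3 lies above the level at which these rules act.
- Adverse-event visit: Table 4 schedules AE assessment before each cycle, not on Day 15.
- Recording rule (10.1.1, 10.3): no withdrawal, treatment or symptoms, so recording rests on the investigator's view of relevance.

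Nothing obliges this event to be recorded, and nothing in 11.2 would count it from the laboratory data.

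**Step 2: scale.** Inputs are the 38% rate (9.1.3) and 33 evaluable or 37 accrued subjects (12.1). The share recorded as adverse events is not in the documents; the range from all to half is an assumption.

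Expected subjects with Grade 3-4 neutropenia = n × 0.38: 33 × 0.38 = 12.54 and 37 × 0.38 = 14.06. The tabulated count x is that number times the share recorded, rounded. The exact (Clopper-Pearson) 95% interval runs from the 2.5% quantile of Beta(x, n − x + 1) to the 97.5% quantile of Beta(x + 1, n − x).

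| Share recorded (assumed) | n = 33 | n = 37 |
|---|---|---|
| All | 12.54 → 13/33 = 39% (23-58%) | 14.06 → 14/37 = 38% (22-55%) |
| Three quarters | 9.4 → 9/33 = 27% (13-46%) | 10.5 → 11/37 = 30% (16-47%) |
| Half | 6.3 → 6/33 = 18% (7-35%) | 7.0 → 7/37 = 19% (8-35%) |

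With half recorded, the upper limit of 35% lies below the 38% used to generate the counts, at either sample size.

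**The case against.** The strongest reply is that the plan is less narrow than it looks. Section 11.1 makes hematology a safety assessment and 11.2 promises to summarize safety data, so counts could fall within that promise. Section 11.2 also has subjects graded each cycle by CTCAE for objective as well as subjective evidence of toxicity, and 12.3 speaks of toxicities rather than adverse events. This stands in part: a reader might infer that laboratory summaries are excluded, and the text does not say so. But it names no laboratory summary, and where 11.2 turns grades into tables it attaches them to adverse-event data.

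The recording rule is also open. Its triggers are examples, and an investigator may judge an asymptomatic Grade 3 count relevant. The AE assessment before the next cycle gives an occasion to do so, and 5.1 says the Day 15 count is there to look for anemia and neutropenia. So a reader might infer that the adverse-event rate is certainly biased downward. The documents support only that under-counting is possible and that the rate depends on judgement.

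Other stronger readings also fail:

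- **All severe cytopenias escape.** Platelets below 50,000/mm³ trigger both notification and a hold. For anemia the documents give no Grade 3 cut-off. The mechanism is shown only for Grade 3 neutropenia.
- **Baseline anemia is unhandled.** Entry is allowed with "HGB equal to or greater than 7g/dL", but 10.1.1 counts only what appears or worsens during observation, which partly deals with it.
- **Only neutropenia treated with G-CSF would be recorded.** Treatment is one of several triggers, so the 9.4% G-CSF use in 9.1.3 does not anchor a recording rate.
- **Comparison with Study 1 would be unfair in a known direction.** Section 9.1.3 does not say whether its 38% came from laboratory values or adverse-event reports.

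Finally, no data are lost: a worst-grade table could be produced at analysis without being planned. That limits the seriousness, but leaves the choice of source to be made after the results are seen.

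**Conclusion.** The point holds as a gap in the planned safety analysis. Followed as written, 11.2 lets the Grade 3 neutropenia rate rest on investigator judgement when an objective source is already being collected. The possible effect is material at this sample size: the same underlying experience could be reported as 39% or 18% of 33 subjects, depending on whether all or half of the events are recorded. Those figures assume that the Study 1 rate applies to this population and that recording lies between half and all. They show scale and do not predict the result. PFS, the sample size and the rules protecting subjects are unaffected, so this is a cheap improvement that should be made rather than a flaw in the design.

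**What to change.** Add a paragraph to 11.2 to this effect:

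> For ANC, platelets and hemoglobin, the worst CTCAE v4.03 grade after the first dose will be derived for each treated subject from all recorded counts, including Day 15, whether or not the value was reported as an adverse event. Results will be shown as a shift from baseline grade, with the proportion of subjects having treatment-emergent Grade 3-4 values and exact 95% intervals.

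State that these laboratory-derived rates are the main source for the frequency of neutropenia, thrombocytopenia and anemia, with the adverse-event tables and the use of G-CSF and red-cell transfusion shown alongside.

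The cost is one paragraph and one programmed table. The CBCs are scheduled in Table 4 and concomitant treatments are recorded under 5.3, so no visit or test is added. The downside is that reported cytopenia rates may look less favourable. No alert, hold or dose rule changes.
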